Outcome ascertainment will be performed in two ways. First, data elements within the PEDSnet common data model (CDM), which comprises structured data extracted from EHRs will be examined to identify the select medical events of interest. Each event will be defined using algorithms that will include diagnostic codes and if needed procedure and medication codes, recorded in the EHR. Second, because not all symptoms, signs, and health problems are included in the structured data as diagnosis codes, a chart review of the EHRs for all eligible study patients will be conducted to examine unstructured text data not captured in the CDM to identify additional patients with the select medical events of interest.

Patients with status epilepticus diagnostic codes in their record will be identified from the cohort and will have their results presented separately in sub tables. They will also contribute to the main study populations. This is to fulfill commitment to examine outcomes in SE patients when exposed to lacosamide. It is assumed that any patients treated with a loading dose of LCM will be more likely to be in SE and proving refractory to treatment than the usual seizure presentation in children.

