**Second step:** Medical charts include the physician notes, laboratory results, EEG recordings and any other original and detailed information that will be used to evaluate or validate the study outcomes. To improve the validity of medical chart review results, at each site these chart reviews will be conducted by experienced healthcare personnel (e.g. nurse clinician) who will be given standardized training before starting the review and a manual of procedures and code set index for assistance. In the case of any queries, an experienced neurologist will be consulted.

The quality control process used to set up the common dataset is described in section 5.7.

The hierarchical level of final reporting of the adverse event outcomes will be agreed with the UCB safety physicians attached to each UCB product, but initially will be reported to include all events. Those not listed (as being specific to LCM) will be included under Section 5.5.1.1 – other diagnoses. In this way all events are captured.

A selection of patients (approximately 10%) will have their charts reviewed (proportion to be agreed post evaluation of final patient numbers and quality of data). As these are retrospective deidentified data, no patient or family consent is required. UCB will not be party to any personal information regarding patients such as name, address or any other identifying variable. Only pertinent medical and treatment data will be collected.

The medical chart reviewers will not be blinded to IV LCM dosage contained within the patient notes as they need to assess dose so that patients can ultimately be categorised into treatment groups at the time of analysis. However, to avoid observation bias, they will be blinded to the full study protocol including title, objectives, and to how study group assignment criteria are applied. Instead, they will be provided instructions as to how to perform data extraction and provided with a case report form to complete. It is assumed based on clinical practice that the information in the medical charts will only indicate the dosage that was prescribed to the patients and will not include language relating to “loading dose/higher dose or recommended dose” per se. Therefore, blinding the medical chart reviewers to the full protocol, will minimize the risk for ascertainment bias.

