Specification for this type of study-specific DQA is part of the analysis planning that goes on between the requestor’s study team and the data science team here. Finally, where external validation of classification is needed, medical records review is available, whether for a sample of the cohort to establish performance characteristics of an algorithm, or for study-specific data capture where needed. When review is done, a common abstraction tool is used, and post-review adjudication is centrally performed, and reviewers receive common training. We do not

routinely use multiple reviewers per record, though it is an option; routine QA would include inter-rater reliability.

Previous studies have applied these quality assessments to the standard to provide data for FDA submission, and deidentified datasets can be provided to the regulator.

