### **5.7.2 Data Validity**

The study will use both the PEDSnet CDM and EHR medical charts data. The validity of the data depends on the source data that was recorded by the physician during each specific encounter. As indicated in the Section 5.7.1, PEDSnet has put in place extensive measures to ensure high validity of the data that is transferred into the CDM. For the chart review, a random sample consisting of 10% of all the EHR medical charts included in the study will be reviewed by a second reviewer and assessed for inter-person variability.

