### 7.4 Reporting obligations

This study uses existing health care databases, in which it is generally not possible to link (i.e., identify a potential causal relationship between) a particular product and medical event for any individual.

This retrospective study (secondary data collection study) is characterized by the secondary use of data previously collected from consumers or healthcare professionals for other purposes. We cannot know if ADR/AEs has been reported previously. Further, initial reporter will not be identifiable (i.e. the 4 elements (compound, AE, Patient, reporter) for a valid Individual Safety Case Report (ICSR) will not be fulfilled.

In addition, this study protocol requires human review of patient-level unstructured data; unstructured data refer to verbatim medical data, including text-based descriptions and visual depictions of medical information, such as medical records, images of physician notes, neurological scans, X-rays, or narrative fields in a database. The reviewer is obligated to report adverse events (AE) with explicit attribution to "Vimpat" that appears in the reviewed information (defined per the patient population and study period specified in the protocol). Explicit attribution is not inferred by a temporal relationship between drug administration and an AE, but must be based on a definite, explicit statement of causality by the original healthcare provider linking drug administration to the AE.

The requirements for reporting safety events on the non-interventional study (NIS) adverse event Report Form to UCB Safety are as follows:

- All serious and non-serious AEs with explicit attribution to "Vimpat" that appear in the reviewed information must be recorded on the chart abstraction form and reported, within 24 hours of awareness, to UCB Safety using the NIS AE Report Form.
- In this study scenarios involving drug exposure that include Vimpat use during pregnancy, during breast feeding, medication error, overdose, misuse, extravasation associated with the use

of “Vimpat” must be reported, within 24 hours of awareness, to UCB Safety using the NIS AE Report Form.

For these safety events with an explicit attribution to or associated with use of, respectively, “Vimpat”, the data captured in the medical record will constitute all clinical information known regarding these AEs. No follow-up on related AEs will be conducted.

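### Chart reviewers abstract adverse events with the dose in view, and withholding the protocol from them does not support the claim that ascertainment bias is minimised for events found only in free text

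*Protocol*

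**What the plan says.** Section 5.4.1 of the protocol is open about the dose: "The medical chart reviewers will not be blinded to IV LCM dosage contained within the patient notes". The reason given is that dose must be abstracted so that patients can be grouped at analysis. The safeguard offered in its place is that "they will be blinded to the full study protocol including title, objectives, and to how study group assignment criteria are applied". The section adds an assumption that notes will record the amount prescribed without labelling it as a loading or higher dose. From this it concludes: "Therefore, blinding the medical chart reviewers to the full protocol, will minimize the risk for ascertainment bias".

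The same review finds outcomes. Section 5.1 says that "a chart review of the EHRs for all eligible study patients will be conducted to examine unstructured text data not captured in the CDM", with the aim of finding further patients with events of interest.

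Section 7.4 gives the person reading the unstructured record a second duty: "The reviewer is obligated to report adverse events (AE) with explicit attribution to" Vimpat. It also requires reporting within 24 hours of a list of exposure scenarios that includes pregnancy and "during breast feeding, medication error, overdose, misuse, extravasation associated with the use" of Vimpat.

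Two checks on the review are described. Section 5.7.2 says that a random 10% of charts "will be reviewed by a second reviewer and assessed for inter-person variability". Section 5.7.1, describing how the network works in general, says that "post-review adjudication is centrally performed, and reviewers receive common training". Neither is stated to be masked to dose.

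**The concern.** The study compares event rates between dose groups. Some outcomes, such as somnolence, dizziness and injection-site discomfort, are often not coded, and whether they are counted depends on how closely someone reads the notes. If a reader who can see a high dose searches that chart harder, the extra events appear as a dose effect.

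The safeguard works only so far as reviewers do not connect dose with the purpose of the review, and two parts of the protocol weaken that. Section 7.4 tells reviewers which drug matters, that its safety is the subject, and that overdose and medication error are to be picked up. Extravasation is on that list and is also a study outcome code, under injection site discomfort in Table 3. Section 5.5.4 expects charts to show individual doses with times, in enough detail to identify a loading dose. An experienced nurse or neurologist could recognise that pattern without a label.

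Little else in the protocol would correct a difference in detection. Inverse probability weighting (Section 5.9.1.1) balances baseline characteristics. Section 5.9.2 treats an unreported diagnosis as absent. None of the four sensitivity analyses in Section 5.9.1.4 separates coded events from events found only in charts. A second review by people who also see the dose would not reveal a tendency they share.

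**Working it through.** The protocol states no figure for abstraction accuracy, so there is none to reproduce. The size can only be shown over an assumed range.

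**Inputs**
- From the protocol: the share of charts reviewed, f, is 1 (Section 5.1, all eligible patients) or about 0.1 (Section 5.4.1). These two statements conflict. The feasibility count is 875 patients (Section 5.9.3), and 10% of 875 is about 88.
- Assumed: true incidence rate ratio (IRR) of 1; a share c of true events captured by codes whatever the reviewer does, c = 0.3 to 0.7; chart sensitivity s1 = 0.9 in the high-dose group and s0 = 0.8, 0.7 or 0.6 in the recommended-dose group; equal group sizes and equal person-time.

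**Formula**

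Expected IRR = [c + f(1 − c)s1] / [c + f(1 − c)s0]

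Example with all charts reviewed, c = 0.3, 0.9 vs 0.6: (0.3 + 0.63) / (0.3 + 0.42) = 0.93 / 0.72 = 1.29. With 10% reviewed: (0.3 + 0.063) / (0.3 + 0.042) = 0.363 / 0.342 = 1.06.

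| Sensitivity, high vs recommended | All charts, c = 0.3 | c = 0.5 | c = 0.7 | 10% of charts, c = 0.3 | c = 0.5 | c = 0.7 |
|---|---|---|---|---|---|---|
| 0.9 vs 0.8 | 1.08 | 1.06 | 1.03 | 1.02 | 1.01 | 1.00 |
| 0.9 vs 0.7 | 1.18 | 1.12 | 1.07 | 1.04 | 1.02 | 1.01 |
| 0.9 vs 0.6 | 1.29 | 1.19 | 1.10 | 1.06 | 1.03 | 1.01 |

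**Chance that a 95% interval wrongly excludes 1** (Wald test on the log IRR, 300 to 875 patients, 10% to 30% of patients with the event). Example at the extreme: 437.5 patients per group and 30% with the event give expected counts of 437.5 × 0.3 × 0.93 = 122.1 and 437.5 × 0.3 × 0.72 = 94.5. The standard error is √(1/122.1 + 1/94.5) = 0.137, and log(1.29)/0.137 ≈ 1.87, so the chance is about 46%. At 0.9 vs 0.6 with all charts reviewed it runs from about 6% to 46% per outcome. With 10% reviewed it is about 5% to 6%. With equal sensitivity in both groups it is 5% throughout and the expected IRR is 1.00.

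The direction, more events at high dose, follows from assuming s1 above s0. It is not a finding from the documents.

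**The case against.** The strongest reply is that Section 7.4 gives away less than it seems to. Section 5.4.1 never relied on reviewers being unaware of the drug, since they abstract its dose. Every patient received IV lacosamide, so knowing that Vimpat safety matters applies to both groups. What is withheld, namely the comparison and the mg/kg cut-offs, stays withheld. This stands: the safeguard is weakened, not removed.

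A reader might also infer that Section 7.4 makes reviewers judge whether a dose was excessive. The text does not say so. It lists scenarios to report, gives no threshold, and for adverse events requires an explicit causal statement from the treating provider. Several listed scenarios have nothing to do with dose. That the overdose prompt would arise mainly in high-dose charts is plausible, but it is not stated.

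A third point concerns size. It is tempting to take the IRR as the plain ratio of sensitivities, for example 0.9/0.8 = 1.13. That holds only if every event comes from chart review. Coded events come first and do not depend on the reviewer, so the diluted figure is 1.03 to 1.08, and lower again if only about 10% of charts are read.

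Finally, training, a manual and a code index, a standard form and a 10% second review are planned, and groups are assigned at analysis. These reduce careless or inconsistent abstraction. They do not mask anyone to dose.

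**Conclusion.** The point holds in a limited form. Reviewers look for free-text outcomes with the dose visible, the only safeguard is withholding the protocol, and Section 7.4 weakens it. The claim that bias is minimised is therefore unsupported for events found only in charts. Coded events are not affected.

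The size is uncertain. It is about 1.03 to 1.29 on a true IRR of 1 if all charts are reviewed, and about 1.00 to 1.06 if about 10% are. Both ranges rest on the assumed sensitivities and coded share. The protocol's two statements on the extent of review leave open which range applies.

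The documents do not show that such bias will occur, nor that the masking fails altogether. The case for change is that a bias of this kind would act on the study's own comparison and is cheap to reduce.

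**What to change.** - Order the abstraction form so that the adverse-event section is completed and locked before the dose section and the Section 7.4 section are opened. All safety reporting is kept.
- Supply the index date and follow-up window from structured data. Section 5.3.3 makes follow-up depend on one or several IV doses, so reviewers would otherwise need the dosing record to know which events count.
- Take dose from the structured administration record, going to free text only if needed, in line with Section 5.5.4.
- Report agreement from the 10% second review by dose group.
- Replace the sentence claiming that bias is minimised with a description of this procedure and of the masking that remains absent.

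The cost is form layout and manual wording. Section 5.4 has the form content agreed before study start, and Section 5.4.1 already plans training and a manual. Abstraction will be slightly slower, and masking stays imperfect where notes mention dose. The fix should not lean on central adjudication, which Section 5.7.1 describes as network practice and not as a commitment of this study, or on dose-redacted extracts, which would be new work.

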## **5.5 Variables**

### **5.5.1 Primary outcome measure**

The following primary variables will be measured to meet the study objectives:

- The incidence rate and incidence rate ratio of cardiac disorders (selected preferred terms (PTs) as described in Section 5.5.5)
- The incidence rate and incidence rate ratio of general disorders and administration site conditions (selected PTs as described in Section 5.5.5)
- The incidence rate and incidence rate ratio of injury, poisoning and procedural complications (selected PTs as described in Section 5.5.5)
- The incidence rate and incidence rate ratio of investigations (i.e. the incidence rate of ECG PR prolongation)
- The incidence rate and incidence rate ratio of skin and subcutaneous tissue disorders (selected PTs as described in Section 5.5.5)
- The incidence rate and incidence rate ratio of drug reactions with eosinophilia and systemic symptoms syndrome (selected PTs as described in Section 5.5.5)
- The incidence rate and incidence rate ratio of severe cutaneous adverse reactions (selected PTs as described in Section 5.5.5)
- The incidence rate and incidence rate ratio of hypersensitivity (selected PTs as described in Section 5.5.5)
- The incidence rate and incidence rate ratio of nervous system disorders (selected PTs as described in Section 5.5.5)
- The incidence rate and incidence rate ratio of metabolism and nutrition disorders (selected PTs as described in Section 5.5.5)

- The incidence rate and incidence rate ratio of psychiatric disorders (i.e. abnormal behavior)

### **5.5.2 Secondary outcome measure**

The secondary variables that will be evaluated in this study include:

- Incidence rate and incidence rate ratio of atrioventricular block
- incidence rate and incidence rate ratio of atrioventricular block complete
- incidence rate and incidence rate ratio of atrioventricular block first degree
- incidence rate and incidence rate ratio of atrioventricular block second degree
- incidence rate and incidence rate ratio of arrhythmia
- incidence rate and incidence rate ratio of bradyarrhythmia
- incidence rate and incidence rate ratio of bradycardia
- incidence rate and incidence rate ratio of cardiac fibrillation
- incidence rate and incidence rate ratio of cardiac flutter
- incidence rate and incidence rate ratio of tachyarrhythmia
- incidence rate and incidence rate ratio of atrial fibrillation
- incidence rate and incidence rate ratio of atrial flutter
- incidence rate and incidence rate ratio of cardiac arrest
- incidence rate and incidence rate ratio of torsade de pointes
- incidence rate and incidence rate ratio of ventricular arrhythmia
- incidence rate and incidence rate ratio of ventricular fibrillation
- incidence rate and incidence rate ratio of ventricular tachyarrhythmia
- incidence rate and incidence rate ratio of palpitations
- incidence rate and incidence rate ratio of chest pain
- incidence rate and incidence rate ratio of gait disturbances
- incidence rate and incidence rate ratio of injection site discomfort
- incidence rate and incidence rate ratio of injection site erythema
- incidence rate and incidence rate ratio of injection site irritation
- incidence rate and incidence rate ratio of injection site pain
- incidence rate and incidence rate ratio of stevens-johnson syndrome
- incidence rate and incidence rate ratio of toxic epidermal necrolysis
- incidence rate and incidence rate ratio of angioedema
- incidence rate and incidence rate ratio of urticaria

- incidence rate and incidence rate ratio of pruritus
- incidence rate and incidence rate ratio of rash
- incidence rate and incidence rate ratio of dizziness
- incidence rate and incidence rate ratio of somnolence
- incidence rate and incidence rate ratio of paresthesias
- incidence rate and incidence rate ratio of loss of consciousness
- incidence rate and incidence rate ratio of syncope
- incidence rate and incidence rate ratio of appetite disorder
- incidence rate and incidence rate ratio of decreased appetite
- incidence rate and incidence rate ratio of diet refusal
- incidence rate and incidence rate ratio of hypophagia
- incidence rate and incidence rate ratio of food aversion

### 5.5.3 Other variables - baseline characteristics

During the baseline period, patient characteristics (e.g. age at index date, gender, ethnicity, PEDSnet health system site, weight), clinical characteristics (i.e. number of previous AEDs and concomitant medications prescribed prior to the index date [AEDs, benzodiazepines and non-AEDs], prevalence of comorbidities, medical procedures such as EEG) will be evaluated. Baseline data will be assessed for IV LCM exposure indications, dosage of IV LCM and preexisting medical events of interest (i.e. cardiac conditions, dermatologic conditions, vascular conditions, injury, poisoning and procedural complications, general disorders and administration site conditions, investigations, drug reaction with eosinophilia and systemic symptoms syndrome, severe cutaneous adverse reactions, hypersensitivity events).

### 5.5.4 Exposure Definition and Measurement

The study population for this study is pediatric patients treated with higher IV LCM doses and recommended initial/maintenance IV LCM dose. Lacosamide will be identified based on prescription or dispensing data from the medications table in the PEDSnet CDM using RxNorm codes ([Table 1 RxNorm codes for Lacosamide](#)), and if needed the free text will be reviewed for further details about the LCM dosage. The equivalent NDC codes have been provided in [Table 2 NDC codes for Lacosamide](#).

**Table 1 RxNorm codes for Lacosamide**

RxNorm CUI	Term	Term Type
1734186	lacosamide injection [Vimpat]	Branded Drug Form
1734189	lacosamide 10 mg/ml injection [Vimpat]	Branded Drug
809984	20 ml lacosamide 10 mg/ml injection [Vimpat]	Quant Branded Drug
809974	20 ml lacosamide 10 mg/ml injection	Quant Clinical Drug

RxNorm CUI	Term	Term Type
1734184	lacosamide injection	Clinical Drug Form
1734188	lacosamide 10 mg/ml injection	Clinical Drug
1186608	Vimpat Injectable Product	Branded Dose Group
1161965	lacosamide Injectable Product	Clinical Dose Group

These subsume exposures that would be described by the following National Drug Codes (NDC) (current and prior) in other data sources as indicated below in [Table 2](#).

**Table 2 NDC codes for Lacosamide**

NDC	Description
00131181067	lacosamide 10 mg/ml injectable solution [Vimpat]
001311810	lacosamide 10mg/ml intravenous injection [Vimpat]
68842081067	lacosamide 10 mg/ml injectable solution [Vimpat]
00091181067	lacosamide 10 mg/ml injectable solution [Vimpat]

The treatment episode for IV LCM will be defined based on the prescription/dispensing information including dosage, formulation, date and time (as available in the database).

The IV LCM loading dose will be defined, where possible, as the single, initial high IV LCM dose which is followed within approximately 12 hours by a subsequent lower maintenance dose.

As we are evaluating IV LCM, which is usually administered in a hospital (inpatient) setting, it is anticipated that in most cases detailed dosage information will be recorded in the patients' medical chart with detailed information on individual IV LCM doses administered, including exact dosage data and time stamps indicating time of administration. This will enable the capture of IV LCM loading dose and the identification of subsequent episodes of IV LCM loading dose exposure.

### 5.5.5 Outcome Definitions and Measurement

The study outcomes will first be defined by querying the PEDSnet CDM for clinically relevant terms associated with these outcomes including signs, symptoms, diagnoses and procedures. These data are coded using Systematized Nomenclature of Medicine-Clinical Terms (SNOMED-CT). SNOMED-CT is an international logic-based, controlled vocabulary used in clinical care that enables meaning-based retrieval of clinical information from electronic health records. SNOMED-CT is based on three types of components: (i) concepts which represent a clinical meaning and have a unique identifier, (ii) descriptions which represent labels of these concepts and (iii) relationships which are binary links between concepts that help define the meaning of each concept. SNOMED-CT has over 300,000 concepts organized according to a hierarchy rooted by 19 high-level classes or axes. Each top-level hierarchy contains sub-hierarchies that further specify a concept.

**Currently, there are no available validated algorithms to identify the study outcomes using the SNOMED-CT vocabulary.** The SNOMED-CT concepts (listed in [Table 3](#) will be reviewed and cased definitions for each outcome will be developed using appropriate algorithms that will

be developed in consultation with clinicians. Second, additional information for these outcomes will be ascertained by medical records review as indicated in Section 5.4. Additionally, the laboratory results may be included during the chart review to confirm any diagnoses. **Sensitivity analyses will be conducted to assess the impact of the case definitions on the effect estimates.**

A number of broad outcomes will be examined in this study and will include:

- Cardiac disorders
- Skin and subcutaneous tissue disorders
- Nervous system disorders
- Metabolism and nutrition disorders
- Psychiatric disorders
- Injury, poisoning and procedural complications
- General disorders and administration site conditions
- Investigations – prolonged PR on ECG
- Drug reaction with eosinophilia and systemic symptoms syndrome
- Severe cutaneous adverse reactions
- Hypersensitivity

Additionally, specific medical events under each broad category will be evaluated as listed below:

- Cardiac Disorders
  - Atrioventricular block
  - Atrioventricular block complete
  - Atrioventricular block first degree
  - Atrioventricular block second degree
  - Arrhythmia
  - Bradyarrhythmia
  - Bradycardia
  - Cardiac fibrillation
  - Cardiac flutter
  - Tachyarrhythmia
  - Atrial fibrillation
  - Atrial flutter
  - Cardiac arrest

- 
- Torsade de pointes
  - Ventricular arrhythmia
  - Ventricular fibrillation
  - Ventricular tachyarrhythmia
  - Palpitations
  - Skin and subcutaneous tissue disorders
    - Stevens-Johnson syndrome
    - Toxic epidermal necrolysis
    - Angioedema
    - Urticaria
    - Pruritus
    - Rash
  - Nervous system disorders
    - Dizziness
    - Somnolence
    - Paresthesias
    - Loss of consciousness
    - Syncope
  - Metabolism and nutrition disorders
    - Appetite disorder
    - Decreased appetite
    - Diet refusal
    - Hypophagia
    - Food aversion
  - General disorders and administration site conditions
    - Chest pain
    - Gait disturbances
  - Injury, poisoning and procedural complication
    - Injection site discomfort
    - Injection site erythema
    - Injection site irritation
    - Injection site pain

Table 3 SNOMED-CT concepts for the study	
Study outcome	SNOMED code
Cardiac Disorders	
Atrioventricular block	SCTID: 233917008
Atrioventricular block complete	SCTID: 27885002
Atrioventricular block first degree	SCTID: 270492004
Atrioventricular block second degree	SCTID: 195042002
Cardiac Arrhythmia (disorder)	SCTID: 698247007
Nodal rhythm disorder (disorder)	SCTID: 71792006
Atrial arrhythmia (disorder)	SCTID: 17366009
Cardiac arrhythmia (disorder)	SCTID: 698247007
Atrio-ventricular node arrhythmia (disorder)	SCTID: 88412007
Neonatal dysrhythmia (disorder)	SCTID: 276513001
Electrocardiogram: sinus arrhythmia (finding)	SCTID: 427393009
Ventricular arrhythmia (disorder)	SCTID: 44103008
Premature beats (disorder)	SCTID: 29717002
Electrocardiographic ventricular arrhythmia (finding)	SCTID: 164893009
Supraventricular arrhythmia (disorder)	SCTID: 72654001
Electrocardiographic supraventricular arrhythmia (finding)	SCTID: 164887001
Bradyarrhythmia	SCTID: 421869004
Supraventricular bradyarrhythmia (disorder)	SCTID: 762534000
Bradycardia	
Electrocardiogram: bradycardia (finding)	SCTID: 426627000
Bradycardia (finding)	SCTID: 48867003
Cardiac fibrillation (disorder)	SCTID: 40593004
Ventricular fibrillation (disorder)	SCTID: 71908006
Atrial fibrillation (disorder)	SCTID: 49436004
Rapid atrial fibrillation (disorder)	SCTID: 314208002
Electrocardiographic atrial fibrillation (finding)	SCTID: 164889003
Electrocardiographic ventricular fibrillation (finding)	SCTID: 164896001
Chronic atrial fibrillation (disorder)	SCTID: 426749004
Paroxysmal atrial fibrillation (disorder)	SCTID: 282825002
Persistent atrial fibrillation (disorder)	SCTID: 440059007
Preexcited atrial fibrillation (disorder)	SCTID: 762247006
Atrial fibrillation and flutter (disorder)	SCTID: 195080001
Non-rheumatic atrial fibrillation (disorder)	SCTID: 233911009
Sustained ventricular fibrillation (disorder)	SCTID: 429243003
Lone atrial fibrillation (disorder)	SCTID: 233910005
Ventricular fibrillation and flutter (disorder)	SCTID: 195083004
Permanent atrial fibrillation (disorder)	SCTID: 440028005

Table 3 SNOMED-CT concepts for the study	
Study outcome	SNOMED code
Cardiac flutter	
Fluttering heart (finding) *	SCTID: 161969004
Ventricular fibrillation and flutter (disorder)	SCTID: 195083004
Atrial fibrillation and flutter (disorder)	SCTID: 195080001
Tachyarrhythmia (disorder)	SCTID: 6285003
Atrial fibrillation	SCTID: 49436004
Atrial fibrillation and flutter (disorder)	SCTID: 195080001
Paroxysmal atrial fibrillation (disorder)	SCTID: 282825002
Rapid atrial fibrillation (disorder)	SCTID: 314208002
Electrocardiographic atrial fibrillation (finding)	SCTID: 164889003
Chronic atrial fibrillation (disorder)	SCTID: 426749004
Persistent atrial fibrillation (disorder)	SCTID: 440059007
Preexcited atrial fibrillation (disorder)	SCTID: 762247006
Atrial fibrillation and flutter (disorder)	SCTID: 195080001
Non-rheumatic atrial fibrillation (disorder)	SCTID: 233911009
Lone atrial fibrillation (disorder)	SCTID: 233910005
Ventricular fibrillation and flutter (disorder)	SCTID: 195083004
Permanent atrial fibrillation (disorder)	SCTID: 440028005
Atrial flutter	SCTID: 5370000
Electrocardiographic atrial flutter (finding)	SCTID: 164890007
Typical atrial flutter (disorder)	SCTID: 720448006
Atypical atrial flutter (disorder)	SCTID: 15964901000119107
Cardiac arrest	SCTID: 410429000
Neonatal cardiac arrest (disorder)	SCTID: 180906006
Bradycardic cardiac arrest (disorder)	SCTID: 703162001
Cardiac arrest due to cardiac disorder (disorder)	SCTID: 423191000
Torsade de pointes	SCTID: 31722008
Electrocardiographic torsades de pointes (finding)	SCTID: 426882006
Ventricular arrhythmia	SCTID: 44103008
Electrocardiographic ventricular arrhythmia (finding)	SCTID: 164893009
Ventricular fibrillation	SCTID: 71908006
Electrocardiographic ventricular fibrillation (finding)	SCTID: 164896001
Sustained ventricular fibrillation (disorder)	SCTID: 429243003
History of ventricular fibrillation (situation)	SCTID: 161513002
Ventricular tachyarrhythmia (disorder)	SCTID: 6624005
Palpitations (finding)	SCTID: 80313002
Palpitations - rapid (finding)	SCTID: 248648003
Bumping heart (finding)	SCTID: 161968007

Table 3 SNOMED-CT concepts for the study	
Study outcome	SNOMED code
Pounding heart (finding)	SCTID: 248657009
Fluttering heart (finding) *	SCTID: 161969004
Palpitations with regular rhythm (finding)	SCTID: 428919002
Intermittent palpitations (finding)	SCTID: 102590007
History of palpitations (situation)	SCTID: 473122004
Skin and subcutaneous tissue disorders	
Stevens-Johnson syndrome (disorder)	SCTID: 73442001
Stevens-Johnson syndrome caused by drug (disorder)	SCTID: 403609001
Stevens-Johnson syndrome, toxic epidermal necrolysis spectrum (disorder)	SCTID: 768946000
Stevens Johnson syndrome AND toxic epidermal necrolysis overlap (disorder)	SCTID: 124911000119100
Stevens-Johnson and toxic epidermal necrolysis overlap syndrome caused by drug (disorder)	SCTID: 724833000
Toxic epidermal necrolysis	
Lyell syndrome (disorder)	SCTID: 768962006
Toxic epidermal necrolysis caused by drug (disorder)	SCTID: 402744003
Stevens-Johnson syndrome, toxic epidermal necrolysis spectrum (disorder)	SCTID: 768946000
Stevens Johnson syndrome AND toxic epidermal necrolysis overlap (disorder)	SCTID: 124911000119100
Stevens-Johnson and toxic epidermal necrolysis overlap syndrome caused by drug (disorder)	SCTID: 724833000
Angioedema	SCTID: 41291007
Giant urticaria (disorder)	SCTID: 400075008
Drug-aggravated angioedema-urticaria (disorder)*	SCTID: 241958006
Angioedema and/or urticaria (disorder)*	SCTID: 404177007
Urticaria	SCTID: 126485001
Acute urticaria (disorder)	SCTID: 402408009
Chronic urticaria (disorder)	SCTID: 51611005
Allergic urticaria (disorder)	SCTID: 40178009
Immunologic urticaria (disorder)	SCTID: 40370006
Contact urticaria (disorder)	SCTID: 19364004
Allergic contact urticaria (disorder)	SCTID: 402304007
Urticaria medicamentosa (disorder)	SCTID: 11012891000119106
Urticaria caused by serum (disorder)	SCTID: 89322006
Drug-aggravated angioedema-urticaria (disorder)*	SCTID: 241958006
Angioedema and/or urticaria (disorder)*	SCTID: 404177007

Table 3 SNOMED-CT concepts for the study	
Study outcome	SNOMED code
History of urticaria (situation) (Prevalent code)	SCTID: 213325008
Dermatographic urticaria (disorder)	SCTID: 7632005
Pruritus	
Pruritic disorders (disorder)	SCTID: 279333002
Itching of skin (finding)	SCTID: 418363000
Generalized pruritus (finding)	SCTID: 276444007
Pruritus caused by drug (disorder)	SCTID: 724843002
Generalized pruritus of unknown etiology (disorder)	SCTID: 403576004
Pruritic rash (disorder)	SCTID: 64144002
Pruritus due to systemic disorder (disorder)	SCTID: 403575000
Pruritus due to neurological disorder (disorder)	SCTID: 724844008
Rash	
Eruption of skin (disorder)	SCTID: 271807003
Eruption (morphologic abnormality)	SCTID: 1806006
Eruption caused by drug (disorder)	SCTID: 28926001
Serum rash (disorder)	SCTID: 213323001
Generalized rash (disorder)	SCTID: 725119006
Localized eruption of skin (disorder)	SCTID: 724877007
On examination - rash present (situation)	SCTID: 268911002
Localized skin eruption caused by drug and medicament (disorder)	SCTID: 200893007
Pseudolymphomatous eruption caused by drug (disorder)	SCTID: 402748000
Generalized skin eruption caused by drug and medicament (disorder)	SCTID: 200892002
On examination - discoid rash (disorder)	SCTID: 164427005
On examination - mouth rash (disorder)	SCTID: 163148009
On examination - itchy rash (disorder)	SCTID: 304386008
On examination - scalp rash (disorder)	SCTID: 395122007
On examination - allergic rash (disorder)	SCTID: 275955005
On examination - erythematous rash (disorder)	SCTID: 135888007
Macular eruption (disorder)	SCTID: 271756005
Bullous eruption (disorder)	SCTID: 271759003
Macular rash (morphologic abnormality)	SCTID: 89757007
Papular rash (morphologic abnormality)	SCTID: 70831001
Pruritic rash (disorder)	SCTID: 64144002
Pustular rash (morphologic abnormality)	SCTID: 48055004
Purpuric rash (disorder)	SCTID: 284078000
Vesicular rash (morphologic abnormality)	SCTID: 53788007

Table 3 SNOMED-CT concepts for the study	
Study outcome	SNOMED code
Blistering eruption (disorder)	SCTID: 247464001
Vasculitic rash (morphologic abnormality)	SCTID: 27006004
Premycotic eruption (disorder)	SCTID: 404102002
Weal (disorder)	SCTID: 247472004
Synchronous rash (finding)	SCTID: 409642009
Morbilliform rash (morphologic abnormality)	SCTID: 50495000
Multimorphic rash (disorder)	SCTID: 301447009
Morbilliform eruption (disorder)	SCTID: 247470007
Maculopapular rash (morphologic abnormality)	SCTID: 47725002
Grade of skin rash (observable entity)	SCTID: 424223007
Maculopapular eruption (disorder)	SCTID: 247471006
Vesiculobullous rash (morphologic abnormality)	SCTID: 14912003
Papulovesicular rash (morphologic abnormality)	SCTID: 4538007
Complaining of a rash (finding)	SCTID: 162415008
Application site rash (disorder)	SCTID: 95371007
Cutaneous hypersensitivity (disorder)	SCTID: 21626009
Nervous System disorders	
Dizziness (finding)	SCTID: 404640003
Dizziness present (situation)	SCTID: 162260006
Dizziness of unknown cause (finding)	SCTID: 429530004
Dizziness due to drug (disorder)	SCTID: 473188002
Dizziness on standing up (finding)	SCTID: 407645004
Postural dizziness (finding)	SCTID: 103017008
Dizziness and giddiness (finding)	SCTID: 271789005
Somnolence	
Drowsiness, function (observable entity)	SCTID: 79519003
Drowsy (finding)	SCTID: 271782001
Complaining of somnolence (finding)	SCTID: 272026007
Daytime somnolence (finding)	SCTID: 141000119100
Excessive somnolence (finding)	SCTID: 372947007
Disorders of excessive somnolence (disorder)	SCTID: 194439006
Somnolence syndrome (disorder)	SCTID: 370971007
Paresthesia (finding)	SCTID: 91019004
Paresthesia of upper limb (finding)	SCTID: 95673003
Facial paresthesia (finding)	SCTID: 95665007
Paresthesia of foot (finding)	SCTID: 309087008
Paresthesia of hand (finding)	SCTID: 309086004
Paresthesia of finger (finding)	SCTID: 762374005

Table 3 SNOMED-CT concepts for the study	
Study outcome	SNOMED code
Transient paresthesia (finding)	SCTID: 135873002
Circumoral paresthesia (finding)	SCTID: 1141007
Paresthesia of lower extremity (finding)	SCTID: 429783005
Paresthesia of right upper limb (finding)	SCTID: 15973701000119104
Paresthesia of right lower limb (finding)	SCTID: 15634791000119106
On examination - paresthesia present (finding)	SCTID: 163707002
Injection site paresthesia (disorder)	SCTID: 95399003
Paresthesia of left lower limb (finding)	SCTID: 15634841000119109
Paresthesia of left upper limb (finding)	SCTID: 15973661000119106
Oral paresthesia (disorder)	SCTID: 95524000
Paresthesia of mucous membrane (finding)	SCTID: 95358009
Paresthesia of tongue (disorder)	SCTID: 95527007
Numbness of skin (finding)	SCTID: 102603008
Burning sensation of skin (finding)	SCTID: 762397008
Prickling sensation of skin (finding)	SCTID: 162248005
Numbness and tingling sensation of skin (finding)	SCTID: 101000119102
Finding of sensation of skin (finding)	SCTID: 297971001
Altered sensation of skin (finding)	SCTID: 247325003
Skin sensation disturbance (finding)	SCTID: 80910005
Complaining of paresthesia (finding)	SCTID: 31048100
Loss of consciousness	
Loss of consciousness (finding)	SCTID: 419045004
Brief loss of consciousness (finding)	SCTID: 32834005
Moderate duration loss of consciousness (finding)	SCTID: 40863000
Prolonged loss of consciousness (finding)	SCTID: 7862002
Syncope	SCTID: 271594007
Syncope and collapse (disorder)	SCTID: 309585006
Metabolism and nutrition disorders	
Appetite disorder	
Non-organic loss of appetite (disorder)	SCTID: 192017004
Appetite problem (finding)	SCTID: 289163007
Appetite symptom (finding)	SCTID: 161824009
Centrally acting appetite suppressant adverse reaction (disorder)	SCTID: 292259006
Altered appetite (finding)	SCTID: 249473004
Eating disorders management (procedure)	SCTID: 386264009
Decrease in appetite (finding)	SCTID: 64379006
Non-organic loss of appetite (disorder)	SCTID: 192017004

Table 3 SNOMED-CT concepts for the study	
Study outcome	SNOMED code
Decreased appetite Decrease in appetite (finding)	SCTID: 64379006
Diet refusal Refusing food (finding) Does not eat (finding) Unable to eat (finding)	SCTID: 105481005 SCTID: 288887001 SCTID: 288885009
Hypophagia Decrease in appetite (finding) Non-organic loss of appetite (disorder)	SCTID: 64379006 SCTID: 192017004
Food aversion Aversion to food or drink (finding) Finding of food aversion and cravings (finding) Sensory aversion to particular foods (finding) Aversion to particular food (finding)	SCTID: 248134002 SCTID: 289143000 SCTID: 16230791000119104 SCTID: 248135001
General disorders and administration site conditions	
